|---------------------------------------|-------------|-------|-------------------|-----------------|-----------------|
| | 65 | 70 | 70 (35 + 35) | 80 (40 + 40) | 90 (45 + 45) |
| Cumulative Dose (mCi/m ²) | 65 | 70 | 70 (35 + 35) | 80 (40 + 40) | 90 (45 + 45) |
| Platelets Grade 4 | 27% | 56.3% | 40% | 50% | 58.8% |
| Platelet Transfusion | 7% | 41% | 0% | 31.3% | 52.9% |
| Neutropenia Grade 4 | 0% | 37.5% | 0% | 31.3% | 29.4% |
| Febrile Neutropenia | 0% | 2.1% | 0% | 0% | 5.8% |

In addition, fractionated dosing allowed concurrent dosing with myelosuppressive chemotherapy:

ii) Phase I trial of fractionated dose ¹⁷⁷Lu–J591 plus docetaxel/prednisone in men with metastatic castration–resistant prostate cancer (42):

Following progression on primary hormonal therapy, chemotherapy can offer symptomatic improvement as well as incremental survival benefit. However, responses are transient and all men eventually suffer from progression of disease as described above with single–agent anti–PSMA based radioimmunotherapy. The combination of taxane chemotherapy with radiotherapy has been used in several diseases because of the radiosensitizing effects of taxane–based chemotherapy. In addition to favorable results from fractionated RIT and the radiosensitizing effects of taxane–based chemotherapy, it is hypothesized that the additional debulking by chemotherapy will overcome some of the limits imposed by the physical characteristics of ¹⁷⁷Lu. Based upon this theory, a phase I trial of docetaxel and prednisone with escalating doses of fractionated ¹⁷⁷Lu–J591 was initiated. 15 men with median age 69.1 (49.3–80.8) were enrolled. The MTD/RP2D of ¹⁷⁷Lu–J591 was 40 mCi/m²x2 doses (delivered with cycle 3 of docetaxel), with 73.3% showing >50% PSA decline, 80.0% reporting >30% PSA decline, and 86.7% with any PSA decline. Predictable, reversible myelosuppression was seen. Even at the highest dose level, no dose limiting toxicity was observed, with short–term / reversible grade 4 neutropenia in 33% and grade 4 thrombocytopenia in 13%.

Aside from the overall rates of dose limiting toxicity, the combined studies have also consistently demonstrated the kinetics of myelosuppression, with nadir neutrophil and platelet counts 28–32 days following the last administered dose of ¹⁷⁷Lu–J591.

With small–molecule radioligand therapy, both the predicted and reported toxicities are much different. One would predict very little myelosuppression, but if it were to occur, it would be

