4. OVERVIEW OF STUDY DESIGN AND METHODOLOGY

4.1 Study Design

This is an open-label, single-center Phase I dose-escalation study designed to determine the dose-limiting toxicity (DLT) and the maximum tolerated dose (MTD) of combination of ¹⁷⁷Lu-J591 and ¹⁷⁷Lu-PSMA-617 in a two-week dose-fractionation regimen. ¹⁷⁷Lu-J591 will be given at a moderate dose previously demonstrated to be safe x2 infusions two weeks apart. For ¹⁷⁷Lu-PSMA-617 the dose escalation will start at 3.7 GBq (100 mCi) and escalate in increments of 1.85 GBq (50 mCi) for each dose to a planned maximum of 9.25 GBq (250 mCi) x2 doses, 2 weeks apart. Should there be unacceptable toxicity at the initial dose level, we will de-escalate to dose level -1 (1.85 GBq / 50 mCi per dose). After the phase I study has established a MTD, the Phase II, single-arm trial will start.

Patients must have documented progressive metastatic CRPC disease based on Prostate Cancer Working Group 3 (PCWG3) criteria in order to be eligible for enrollment. Upon meeting the inclusion and exclusion criteria and signing the informed consent and HIPPA form, subjects will undergo the screening. As part of the screening, subjects will get a single dose of ⁶⁸Ga-PSMA-HBED-CC and will have a PET/CT. Nuclear Medicine physician(s) will review the PET/CT scans to document PSMA expression at tumor site(s).

Subjects will have Lutetium-177 Planar/SPECT Imaging on Day 8 (±1 day) after the first dose of ¹⁷⁷Lu-J591 + ¹⁷⁷Lu-PSMA-617. Optimal images will be performed on selected consenting subjects between the initial treatment visit #1 on Day 1 and Day 4 and prior to treatment visit #2 on D15 ±1. Subjects will be closely monitored for AEs (weekly x2 weeks, then every 2 weeks for one month, at 8 and 12 weeks, and then every 4 weeks for next 3 months).

Upon completion of investigational treatment with dose-fractionation regimen of the combination of ¹⁷⁷Lu-J591 + ¹⁷⁷Lu-PSMA-617, subjects will undergo ⁶⁸Ga-PSMA-HBED-CC injection and same day PET/CT at the end of study visit to document treatment response. Subsequently survival data and additional treatment(s) information will be captured from their routine Standard of care (SOC) visits.

Table 14: Phase I dose-escalation plan for combination of ¹⁷⁷Lu-J591 + ¹⁷⁷Lu-PSMA-617:

| ¹⁷⁷Lu–J591 + ¹⁷⁷Lu–PSMA–617: Dose escalation (per dose) | | |
|--|----------------------------------|----------------------------------|
| | ¹⁷⁷Lu–J591* | ¹⁷⁷Lu–PSMA–617 |

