6.1 Schedule of Evaluations

Table 15: Schedule of trial events:

| | Screening | Treatment Visit 1 | Imaging visit | Treatment Visit 2 | F/U Visit 1 | F/U Visit 2 | F/U Visit 3 | F/U Visit 4 | F/U Visit 5 | Scan / Efficacy Visit | Short-Term F/U ^k | Long-Term F/U |
|--|-----------|-------------------|---------------|-------------------|-------------|-------------|-------------|-------------|-------------|-----------------------|-----------------------------|----------------|
| Informed Consent | x | | | | | | | | | | | |
| Demographics | x | | | | | | | | | | | |
| Medical History | x | x | x | x | x | x | | x | | x | x | |
| Physical Exam | x | x | x | x | x | x | | x | | x | x | |
| Performance Status | x | x | x | x | x | x | | x | | x | x | |
| Vital Signs ^a | x | x | x | x | x | x | | x | | x | x | |
| PRO ^l | x | x | x | x | x | x | | x | | x | x ^l | |
| CBC with diff, plts ^b | x | x | x | x ^c | x | x | x | x | x | x | x | |
| Serum Chemistry ^d | x | x | x | x | x | x | x | x | x | x | x | |
| PSA | x | x | | x | | x | | x | | x | x | |
| LDH | | x | | x | | x | | x | | x | x | |
| Testosterone | x | | | | | | | | | x | | |
| CTC Count ^e | x | x ^e | | | | | | | | x | | |
| CTC for Research ^f | x | x ^f | | | | | | | | x | | |
| Cell-Free DNA Research sample ^g | x | x ^g | | | | | | | | x | | |
| Immune research sample ^m | x | x ^m | | | | | | | | x | | |
| ⁶⁸ Ga-PSMA infusion & PET CT | x | | | | | | | | | x | | |
| Radiographic evaluation ^h | x | | | | | | | | | x | x ^h | x ^h |
| ¹⁷⁷ Lu-J591 infusion | | x | | x | | | | | | | | |
| ¹⁷⁷ Lu-PSMA-617 infusion | | x | | x | | | | | | | | |

| | | | | | | | | | | | | |
|---|---|---|----------------|----------------|---|---|--|---|--|---|---|---|
| ¹⁷⁷ Lu-Planar/SPECT imaging ⁱ | | | x ⁱ | x ⁱ | | | | | | | | |
| Archival Tissue | x | | | | | | | | | | | |
| Adverse Event Monitoring | | x | x | x | x | x | | x | | x | x | |
| Concurrent Medications | x | x | x | x | x | x | | x | | x | x | |
| Survival Assessment ^j | | | | | | | | | | | | x |

- a: Vital signs will include height and weight during screening and at least weight thereafter
- b: Any subject with grade >2 neutropenia or thrombocytopenia at any time point will be followed at least weekly until resolution to grade 1

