- PSA (Follow up visits 2 & 4)
- LDH (Follow up visits 2 & 4)
- Adverse event evaluation
- Concomitant medications

6.1.2.3 Follow-up lab visits: Follow up Visit 3 (Day 43 \pm 3); Follow up Visit 5 (Day 71 \pm 3)

- CBC with differential and platelet count
- CMP (with direct bilirubin with known Gilbert's syndrome)
- PSA
- LDH

Lab visits may be performed at any CLIA certified lab

6.1.3. Efficacy Evaluation (scan) Visit (Day 85 ± 7; note that these study procedures are not expected to occur on a single day)

The following procedures must be completed during the efficacy visit(s):

- Targeted Physical Examination with vital signs and weight
- Medical History
- Brief Pain Inventory, FACT-P
- ECOG Performance Status
- CBC with differential and platelet count
- CMP (with direct bilirubin with known Gilbert's syndrome)
- PSA
- LDH
- Testosterone
- CTC count via CellSearch methodology
- CTC for research
- Cell-Free DNA BCT[®] Research blood sample
- Immune research blood sample
- Same standard radiographic imaging modality as baseline (CT/MRI and bone scan +/- CXR)
- Single intravenous dose of ⁶⁸Ga-PSMA-HBED-CC (5±2mCi or 185±74MBq)
- PET/CT scan will be obtained between 1 and 3 hours post-injection of ⁶⁸Ga-PSMA-HBED-CC
- Adverse event evaluation
- Concomitant medications
- Concomitant procedures

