12.5 Analysis of Endpoints

12.5.1 Analysis of Primary Endpoints

The primary endpoint will be the proportion of subjects with DLT from Treatment Visit #1 through End of Study (Efficacy/scan) Visit. The MTD is the highest dose amongst the different dose-level cohorts in this study at which no more than 1 out of 6 subjects in a cohort experience DLT.

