12.6 Reporting and Exclusions

12.6.1 Evaluation of toxicity

All subjects will be evaluable for toxicity from the time of their first infusion with ⁶⁸Ga-PSMA-HBED-CC as well as when they receive their first treatment with ¹⁷⁷Lu-J591 + ¹⁷⁷Lu-PSMA-617 and up to 30 days after their last treatment. The distributions of the maximum observed grade toxicity will be tabulated for each type of toxicity and presented by dose level and overall. Results will be summarized with descriptive statistics.

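### Section 12.6.1 closes toxicity evaluability 30 days after last treatment, inside the stated J591 nadir and about 40 days before the DLT window ends

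*Combined protocol and SAP*

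**What the plan says.** Section 12.6.1 starts toxicity evaluability at the first infusion and continues it "and up to 30 days after their last treatment". Its next sentence is the tabulation rule: "The distributions of the maximum observed grade toxicity will be tabulated for each type of toxicity and presented by dose level and overall". Safety by CTCAE 4.0 is a secondary objective (1.2). Section 12.5.2, on secondary endpoints, does not mention it, so 12.6.1 is the only place where a safety table is specified.

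Three other parts of the protocol use or imply a longer period:

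- **DLT endpoint (12.5.1):** "The primary endpoint will be the proportion of subjects with DLT from Treatment Visit #1 through End of Study (Efficacy/scan) Visit". Section 6.1.3 puts that visit at Day 85 ± 7.
- **Marrow kinetics (2.7, part B):** the earlier J591 studies "demonstrated the kinetics of myelosuppression, with nadir neutrophil and platelet counts" 28 to 32 days after the last dose.
- **Adverse event monitoring (4.1):** after the early visits it continues "at 8 and 12 weeks, and then every 4 weeks for next 3 months". In Table 15 the row "Adverse Event Monitoring" is marked at the Efficacy visit and in short-term follow-up, which footnote k runs to 6 months from first treatment. The procedure list in 6.1.4 for those same visits omits an adverse event evaluation.

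**The concern.** The trial has one period for deciding whether a toxicity is dose-limiting and a shorter one for deciding whether a subject is evaluable for toxicity. The shorter one ends around the time J591 marrow toxicity is expected to be deepest.

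Grade 4 cytopenia is an expected event here. Table 11 reports grade 4 thrombocytopenia in 40% at 35 + 35 mCi/m² and 50% at 40 + 40 mCi/m² of J591 alone. Under the amended dosing this trial gives 36.5 + 36.5 mCi/m² with a second radionuclide. Under 6.2.10, grade 4 hematologic toxicity that is at least possibly related is a DLT.

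What is at stake is agreement between two safety outputs for the same dose level. If 12.6.1 is applied as written, a DLT that helped set the MTD could be absent from the maximum-grade table, and the tabulated profile could look milder than the data used to choose the dose.

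**Working it through.** **The plan's own figure.** The only design figure that depends on complete DLT capture is the 3+3 escalation table in 4.2 and 12.1. The formula is P(escalate) = (1−p)³ + 3p(1−p)² × (1−p)³. At p = 0.30 this is 0.343 + 0.441 × 0.343 = 0.494. Across p = 0.05, 0.10, 0.20, 0.30, 0.40, 0.50 and 0.60 it gives 0.973, 0.906, 0.709, 0.494, 0.309, 0.172 and 0.082. These match the stated 0.97, 0.91, 0.71, 0.49, 0.31, 0.17 and 0.08. Nothing below disputes them.

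**Inputs.** Second dose on Day 15 ± 1 (6.1.2); maximum hold of 2 weeks (Table 15, footnote c); evaluability to last dose + 30 days (12.6.1); nadir at last dose + 28 to + 32 days (2.7, part B); DLT window to Day 85 ± 7 (12.5.1 with 6.1.3).

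**Dates.** End of evaluability = last dose + 30. Gap = 85 − end of evaluability.

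| Last dose | Evaluability ends | Nadir | Gap to Day 85 |
|---|---|---|---|
| Day 15 | 15 + 30 = Day 45 | Day 43–47 | 40 days |
| Day 29 (held 2 weeks) | 29 + 30 = Day 59 | Day 57–61 | 26 days |
| Day 1 only | 1 + 30 = Day 31 | Day 29–33 | 54 days |

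The cutoff falls inside the nadir for any last-dose day, because 30 lies between 28 and 32. Allowing for visit windows without a hold, the gap runs from 78 − 46 = 32 days to 92 − 44 = 48 days. Six months from Day 1 is about Day 183, which is 183 − 45 = 138 days after the cutoff.

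**Scheduled assessments after a Day 15 second dose.** The three short-term visits fall at 85 + 28k, that is Days 113, 141 and 169.

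- CBC: Days 22, 29 and 43 are inside; Days 57, 71, 85, 113, 141 and 169 are outside (6 of 9).
- Adverse event evaluation: Days 22 and 29 are inside; Days 57, 85, 113, 141 and 169 are outside (5 of 7).

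**A concrete case.** A man has grade 2 platelets at the Day 43 laboratory visit. Footnote b triggers weekly counts only above grade 2, so his next scheduled CBC is Day 57. Grade 4 is first seen then, and is judged possibly related.

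- Under 12.5.1 and 6.2.10: Day 57 is before Day 85, so this is a DLT.
- Under 12.6.1: Day 57 is after Day 45, so it lies outside the period in which he is evaluable for toxicity.

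**The case against.** The strongest reply is that little is lost in practice, and much of it stands.

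- **The dose decision is intact.** A reader might infer that DLTs after Day 45 would be missed and escalation made too easy. The documents do not support that. Section 12.5.1 sets the DLT window explicitly, 12.6 provides for safety review in real time and before each escalation, and section 14 has the DSMB notified after each cohort.
- **The nadir is observed.** A reader might also infer that nadir cytopenia goes unseen. Section 6.1.2 lists "Follow-up lab visits: Follow up Visit 3" at Day 43 ± 3 with a CBC, normally inside the 30 days. Footnote b adds: "Any subject with grade >2 neutropenia or thrombocytopenia at any time point will be followed at least weekly until resolution to grade 1". Cytopenia is graded from the CBC, so the lack of an adverse event evaluation between Days 29 and 57 matters little for marrow toxicity.
- **Late events are not left uncollected.** It is tempting to add that new renal or marrow events after progression go unrecorded. But 6.1.5 and footnote j collect relevant medical history until death, and 6.1.5 requires an update at least every 6 months. Sections 11.1, 13.1.3, 13.2.1 and 13.2.2 cover adverse event and SAE recording and reporting with no 30-day limit. Named fields for such events would be a matter of detail, not the correction of a fault.
- **The day and visit counts do not measure lost toxicity.** They describe the calendar, and the visit shares depend on where counting starts: from Day 8 they become 6 of 11 CBCs and 5 of 9 adverse event evaluations. The last three visits also require no radiographic progression, withdrawal or new treatment.
- **The tabulation sentence has no cutoff of its own.** This is correct, and 13.3 follows reported events to resolution or stabilization. The plan does not say that a peak grade reached after Day 45, in an event that began earlier, is discarded.

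The last point does not remove the problem. The table follows directly on the sentence saying when subjects are evaluable for toxicity, and no other period is given for it. An analyst would have to choose between Day 45, Day 85 and 6 months without guidance.

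**Conclusion.** The point holds as a fault in the analysis window, not in data collection or dose-finding. Section 12.6.1 conflicts with 12.5.1 by 40 days for a Day 15 second dose (26 days after a two-week hold) and with adverse event monitoring by about 138 days. Its cutoff falls inside the protocol's own nadir whichever day the last dose is given.

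The certain effect is ambiguity in the only table specified for the CTCAE safety objective. The possible effect is that DLTs first seen after Day 45 are missing from it. This rests on reading the evaluability sentence as setting the period for the table that follows. How many maximum grades would change cannot be estimated, because Table 11 gives grade 4 rates without times of onset. No sample size or escalation figure changes.

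**What to change.** In 12.6.1, replace "and up to 30 days after their last treatment" with evaluability and maximum-grade tabulation through the Efficacy/scan visit, so that the period matches 12.5.1. Add a descriptive summary by dose level of events from that visit to the end of the 6-month short-term follow-up, flagging those that occur after subsequent therapy. In 6.1.4, add adverse event evaluation to the procedure list, where Table 15 already marks it.

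The cost is a wording change and one more descriptive table. No visits, samples or patients are added. The drawback is that some later events will be confounded by disease or new therapy, so the post-Efficacy-visit summary should be kept separate and read descriptively.

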6. STUDY PROCEDURES

Screening assessments and study procedures outlined in this section can only be performed after obtaining informed consent. All on-study visits and dosing should be scheduled from Day 1 (date of the first infusion) on the study. It is very important that protocol procedures are performed at the time-points stipulated below. When it is not possible to perform, the study visit at the exact time-point, the visit maybe performed within the acceptable visit window as defined in the visit-specific section below.

After obtaining informed consent from enrolled subject(s), screening and study related treatment procedures will be performed as outlined in **Table 15** and described in detail in **Section 6.1**.

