6.2.10 Managing toxicity

NCI CTCAE version 4.0 is used to grade all adverse events.

- Grade ≥ 2 thrombocytopenia or neutropenia within 24 hours of the second dose of ^{177}Lu -J591 + ^{177}Lu -PSMA-617 (Treatment Visit #2) requires a subject's treatment to be held until the toxicity has resolved to least grade 1. If the toxicity has not resolved after 2 weeks of monitoring, the subject's ^{177}Lu -J591 + ^{177}Lu -PSMA-617 treatment will be permanently discontinued and will be termed dose-limiting toxicity.

Dose-limiting toxicity (DLT) is defined as:

- Grade 4 hematologic toxicity that is deemed at least possibly related to ^{177}Lu -J591 and/or ^{177}Lu -PSMA-617 will be termed dose-limiting toxicity
- Any grade > 2 non-hematologic toxicity deemed to be at least possibly related to ^{177}Lu -J591 and/or ^{177}Lu -PSMA-617 will require a subject's ^{177}Lu -J591 + ^{177}Lu -PSMA-617 treatment to be permanently discontinued and will be termed dose-limiting toxicity.
 - A 1-grade increase in a pre-existing from grade 2 to grade 3 will only be considered a DLT if probably or definitely related to study drug

Maximum Tolerated Dose (MTD) is defined as:

- The dose that produces an “acceptable” level of toxicity or that, if exceeded, would put subjects at “unacceptable” risk for toxicity. Definition of the MTD usually relies on the sample, as MTD is defined as the dose level at which no more than two patients out of six experienced dose-limiting toxicity (DLT).

Note: Toxicities as described above will be considered DLT if they are at least possibly related to ^{177}Lu -J591, ^{177}Lu -PSMA-617 or ^{68}Ga -PSMA-HBED-CC as judged by the investigator (see note above re: 1-grade increases in which case only probably/definitely related toxicities will be deemed DLT). Attribution will be reviewed by the study chair and discussed with the medical monitor if there are questions about severity or attribution.

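### The 30-day toxicity window in 12.6.1 closes within the reported marrow nadir and about 40 days before the DLT window ends, so the maximum-grade table can omit or under-grade late toxicity that counts as a DLT

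*Combined protocol and SAP*

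**What the plan says.** Section 12.6.1 opens evaluability for toxicity at the first 68Ga infusion and at the first 177Lu treatment. It closes it, and defines the summary table, in these words: "up to 30 days after their last treatment. The distributions of the maximum observed grade toxicity will be tabulated for each type of toxicity". The table is to be shown by dose level and overall. The section does not say whether an event is placed by its onset or by the date of each grade.

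The phase I primary endpoint in 12.5.1 uses a different period: "The primary endpoint will be the proportion of subjects with DLT from Treatment Visit #1 through End of Study (Efficacy/scan) Visit". Section 6.1.3 places that visit as follows: "Efficacy Evaluation (scan) Visit (Day 85 ± 7". Section 6 counts visits from the first infusion: "All on-study visits and dosing should be scheduled from Day 1 (date of the first infusion) on the study".

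On marrow kinetics, section 2.7 reports from the earlier 177Lu-J591 studies "nadir neutrophil and platelet counts 28–32 days following the last administered dose". Under 6.2.10, grade 4 hematologic toxicity that is at least possibly related is a DLT. So is cytopenia that blocks the second dose and has not resolved after two weeks: "treatment will be permanently discontinued and will be termed dose-limiting toxicity".

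Footnote b of Table 15 adds counts for severe cytopenia: "Any subject with grade >2 neutropenia or thrombocytopenia at any time point will be followed at least weekly until resolution to grade 1".

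**The concern.** The two windows cover the same patients and partly the same events, but they end about 40 days apart, and no text reconciles them. The shorter one ends when counts are expected to be near their lowest.

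Safety by CTCAE grade is a secondary objective (1.2), and cytopenia is the expected toxicity. Table 11 reports grade 4 platelets in 40% at 35 + 35 mCi/m² of 177Lu-J591 and in 50% at 40 + 40. From cohort 1a on, this trial gives 36.5 + 36.5 with a second radiolabelled agent. The maximum-grade table is the toxicity summary that 12.6.1 specifies. Section 12.5.2, on secondary endpoints, gives no analysis of safety, and the descriptive fallback in 12.1 is written for phase I.

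At stake is whether the reported worst grade is the one the patient actually had. Also at stake is whether the toxicity table and the DLT count for one cohort agree.

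**Working it through.** **Inputs.** Second dose on Day 15 ± 1 (6.1.2). It may be held for up to 2 weeks, so to about Day 29 (Table 15 footnote c). Close of the toxicity window: last dose + 30 (12.6.1). Nadir: last J591 dose + 28 to + 32 (2.7). End of the DLT window: Day 85, range 78–92 (12.5.1, 6.1.3). Scheduled CBCs after dose 2: Days 22, 29, 43, 57, 71 and 85 (6.1.2, 6.1.3).

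**Formulas.** Close = L + 30, where L is the day of the last dose. Nadir = L + 28 to L + 32. Gap = Efficacy visit day − (L + 30).

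| Last dose | Close | Nadir | Gap to Day 85 (Day 78 to Day 92) | Scheduled CBCs after the close |
|---|---|---|---|---|
| Day 14 | 44 | 42–46 | 41 (34–48) | 57, 71, 85 |
| Day 15 | 45 | 43–47 | 40 (33–47) | 57, 71, 85 |
| Day 16 | 46 | 44–48 | 39 (32–46) | 57, 71, 85 |
| Day 29 (held 2 weeks) | 59 | 57–61 | 26 (19–33) | 71, 85 |
| Day 1 (dose 1 only) | 31 | 29–33 | 54 (47–61) | 43, 57, 71, 85 |

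The close and the nadir both count from the last dose, so every row closes mid-nadir: post-dose days 28–30 are inside and days 31–32 are outside. With the second dose on schedule, the gap to the DLT window is 40 days, or 32–48 over all visit windows.

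**Blood counts.** With dose 2 on Day 15, three of the six scheduled CBCs after it lie outside. The Day 43 visit may fall on Days 40–46, which is 25–31 days after dose 2, so a visit on Day 46 would also be outside.

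**Adverse event evaluations.** Table 15 leaves the row blank at follow-up visits 3 and 5: "Adverse Event Monitoring | | x | x | x | x | x | | x | | x | x". The narrative in 4.1 has checks every two weeks for a month after the first two weeks, which implies one near Day 43. The two sources therefore differ on Day 43, but under either one the evaluations on Days 57 and 85 are outside.

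**Effect on the table.** Take platelets at grade 2 on Day 43. Footnote b is not triggered, and the next scheduled CBC is Day 57, 57 − 43 = 14 days later. Suppose a related grade 4 count is first recorded then. It is a DLT under 6.2.10 and 12.5.1. In the 12.6.1 table:

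- if the window is a cut, the patient stays at grade 2;
- if events go by onset, an event that began by Day 45 can carry its later grade 4, but a cytopenia first seen after Day 45 is left out;
- if the table has no time limit, grade 4 appears, but the 30-day limit then has no effect.

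The first reading under-grades this patient. The second leaves out any patient whose cytopenia is first seen after Day 45.

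**The case against.** The best counter-argument is that the 30 days define who is evaluable, while the next sentence tabulates the highest grade observed and carries no limit of its own. That fits 13.1.3, which logs all adverse events, and 13.3, which follows them to resolution or stabilization. But it leaves the limit with nothing to do, and a programmer given 12.6.1 would reasonably apply it.

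Several other points stand and set the size of the problem.

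- The nominal Day 43 CBC falls on post-dose day 28, the start of the nadir, and grade >2 there brings at least weekly counts. Many severe cytopenias will therefore be recorded inside the window. A severe count first recorded on Day 57 comes 57 − 47 = 10 days after the stated nadir ends. It is possible, because no count is scheduled in between, but it is not the typical course.
- The 28–32 days come from 177Lu-J591 without PSMA-617. The mismatch with the DLT window does not depend on them.
- An onset rule would carry the later grade in the example above. So a reader should not infer that a Day 57 grade 4 is bound to be missing, only that it can be.

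A reader might also infer that the DLT count, the MTD or escalation is compromised. The documents do not support that: 12.5.1 governs DLTs through the Efficacy visit, and the interim analysis section has safety reviewed in real time before each escalation. Nor are safety data lost. Counts and adverse event evaluations continue past Day 45, and 12.1 allows further summaries or listings in phase I. A subject whose second dose is abandoned for unresolved cytopenia is already a DLT under 6.2.10, although his later counts still lie outside the table window.

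**Conclusion.** The point holds as a defect in the tabulation rule. The window in 12.6.1 ends on Day 45 with dose 2 on Day 15. That is within the nadir of Days 43–47 and 40 days (32–48) before the DLT window ends. The maximum-grade table can therefore omit or under-grade a late toxicity, and it can disagree with the DLT count for the same cohort.

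The number of affected events cannot be derived, because the documents give no distribution of time to grade 4. The share of days or visits outside the window is not an estimate of it. The conclusion rests on 12.6.1 being applied either as a cut or by onset; on the onset reading it is limited to events first seen after the close. The nadir overlap also assumes that J591 kinetics carry over to the combination. The consequence is confined to reported safety, but the inconsistency is in a stated rule and is cheap to remove.

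**What to change.** In 12.6.1, run the toxicity window from the first 68Ga infusion through the Efficacy visit (Day 85 ± 7) for every treated subject, including those who receive only dose 1, to match 12.5.1. State that the table shows the maximum grade reached in that window, by dose level, with attribution shown in the categories of 13.1.2.

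This closes the gap to 0 days. It needs no new visits or data items: the CBCs on Days 57, 71 and 85 and the adverse event evaluations on Days 57 and 85 are already scheduled. It does not delay escalation.

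The cost is that more events due to disease or to subsequent therapy enter the table. Showing attribution handles this only in part.

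A count of subjects whose neutrophils or platelets have not returned to grade ≤1 at the Efficacy visit would be a useful optional addition, since a maximum-grade table says nothing about recovery. It is not needed to cure the mismatch.
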